ESTIMATED NUMBER OF PATIENTS/GEOGRAPHIC REGIONS	
200 evaluable (220 total) relapsed/refractory pediatric cancer patients. Additional patients may enroll through compassionate access if no other treatment options are available.
 
Patients will enroll at:
 
Arnold Palmer Children's Hospital, FL St. Louis University/Cardinal Glennon Children's Medical Center, MO Helen DeVos Children's Hospital, MI Levine Children's Hospital, NC Connecticut Children's Medical Center, CT Children's Mercy Hospital, Kansas City MO Rady Children's Hospital of San Diego, CA Medical University of South Carolina, SC Monroe Carrell Jr. Children's Hospital at Vanderbilt, TN Kapiolani Medical Center for Women and Children, HI Dell Children's Hospital, TX Texas Children's Hospital, Baylor College of Medicine, TX Primary Children's Hospital, UT Children's Hospital and Clinics of Minnesota, MN Penn State Milton S. Hershey Medical Center and Children's Hospital, Hershey, PA Arkansas Children's Hospital – Little Rock, AR 
International Sites
 American University of Beirut Medical Center, Lebanon La Timone; Marseille, France

LENGTH OF STUDY	Accrual to this study is estimated to be approximately 3-4 years.
STUDY ASSESSMENTS	Refer to Table of Assessments for timing of study procedures.
CRITERIA FOR EVALUATION	
Feasibility Measures: Primary objective: The definition of feasibility for this study will include: “Enrollment onto study, genomic profile, analysis and report generation completed, tumor board held with treatment decision, treatment review completed, start of treatment, and completion of 1 cycle of therapy.”
 
Efficacy Measures: Secondary objectives Response: To determine the overall response rate (ORR) by the presence of radiologically assessable disease by cross-sectional CT or MRI imaging and/or by MIBG or PET scans.
 
 ◆ Duration of response, defined as the period of time from when measurement criteria are met for complete response (CR) or partial response (PR), whichever is first recorded, until the first date that recurrent or progressive disease (PD) is objectively documented (taking as reference for PD the smallest measurements recorded since the treatment started) ◆ The assessment of response will include the initial measurable

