	
targets and will be performed after cycle 2, then after every other cycle.
 
 • A subject will be defined as a responder if CR/PR is observed at any time of the treatment • Clinical response will be seen if stable disease and decrease in tumor markers by $\geq 50\%$ or CR of bone marrow. • Time to progression, defined as the period from the start of the treatment until the criteria for progression are met taking as reference the screening measurements • Comparisons of ORR and PFS for the first and second cohorts of 100 patients (i.e., those who enroll prior to versus after the implementation of Amendment 3.0, respectively) will be performed. 
Safety Measures: Secondary objectives
 
 • Safety analysis will be conducted on all subjects who have received at least one dose of therapy, and will include the frequency of all reported adverse events and laboratory abnormalities as well as frequency of dose interruptions, dose reductions and treatment discontinuation.
STATISTICS/SAMPLE SIZE ESTIMATE	
200 evaluable subjects
 
Patients who enroll following implementation of Amendment 3.0 (second cohort of 100 patients) will have their tumor biopsies analyzed using an updated Drug Prediction Report (Appendix III). Overall Response Rate (ORR) and Progression Free Survival (PFS) for this group will be compared to those of the first 100 patients who received treatment based upon the original Drug Prediciton Report and Pharmacopeia Library.

TABLE OF PROCEDURES AND ASSESSMENTS

Procedure	Screening	Cycle 1 Day 1	Cycle 1 Day 8	Cycle 1 Day 15	Cycle 1 Day 22 (if applicable)	Subsequent Cycles Day 1	Off Therapy/ 30 Day Follow-up
Informed consent	X						
Demographics	X						
Medical history	X	X	X	X	X	X	
Baseline Symptom Form	X	X					
Concurrent meds	X	X				X	X
Physical exam	X	X	X	X	X	X	X
Vital signs	X	X	X	X	X	X	X
Height	X	X				X	
Weight	X	X				X	X
Karnofsky or Lansky play score	X	X		X		X	X
CBC w/diff,	X	X	X	X	X	X	X
Serum chemistry *	X	X		X		X	X
Tumor Markers **	X	X				X	X
Adverse events			X	X	X	X	X
Surgical resection &/or diagnostic biopsy	X						
MRI or CT***	X						
MIBG/PET ***	X						
Bone Marrow (any subject suspected to have BM disease) ^	X						
B-HCG	X						
EKG (as indicated)		X					

* Serum electrolytes, BUN, Creatinine, Bilirubin, ALT, AST

**LDH and/or Specific Tumor Markers for defined disease (if available)

***Type of scan as indicated for disease type

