2.2 Secondary Objectives

- ◆ To determine the activity of treatments chosen based on:
 - Overall response rate (ORR)
 - Progression free survival (PFS)
- ◆ To continue to evaluate the safety of allowing a molecular tumor board to determine individualized treatment plans
- ◆ (Voluntary) To explore the relationship between tumor phenotype/genotype and response by permitting use of tumor tissue in a correlative biologic study
- ◆ To compare PFS interval to PFS intervals of previous chemotherapy regimens since relapse for each subject.
- ◆ Sub analysis examination of disease types.

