- **Progressive Disease (PD):** At least a 20% increase in the sum of the disease measurements for measurable lesions, taking as reference the smallest disease measurement recorded since the start of treatment (nadir), and minimum 5 mm increase over the nadir or the appearance of one or more new lesions.

Response Criteria for Subjects with Bone Marrow Disease:

- Those subjects with morphologic evidence of disease by routine H and E staining (NSE staining only is not evaluable) will be evaluable to assess bone marrow response.
- **Complete response:** No tumor cells detectable by routine morphology on two consecutive bilateral bone marrow aspirates and biopsies done at least three weeks apart after study entry.
- **Progressive disease:** Tumor seen on morphology on two consecutive bone marrows done at least three weeks apart in subjects who had NO tumor in bone marrow at study entry. (Note: Subject may be declared as progressive disease in bone marrow after only one diagnostic bone marrow at the discretion of the treating physician after discussion with the study chair.)
- **Stable disease:** Persistence of an amount of tumor in the bone marrow by morphology that does not meet criteria for either complete response or progressive disease.

Response Criteria for Subjects with MIBG or PET Positive Lesions

- Subjects who have a positive MIBG or PET scan at the start of therapy will be evaluable for MIBG or PET response. All MIBG's and PET scans will be performed at the research institution and then centrally reviewed.
- **Complete response** = complete resolution of all positive lesions
- **Partial response** = resolution of at least one positive lesion, with persistence of other MIBG positive lesions.
- **Stable disease** = no change in scan in number of positive lesions (includes subjects who have same number of positive lesions but decreased intensity)
- **Progressive disease** = Development of new positive lesions

The intensity of MIBG uptake is not to be considered in the above institutional evaluation.

Duration of response:

Duration of response is defined as the period of time from when measurement criteria are met for complete response (CR) or partial response (PR), whichever is first recorded, until the first date that recurrent or progressive disease (PD) is objectively documented (taking as reference for PD the smallest measurements recorded since the treatment started).

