The assessment of response will include the initial measurable targets and will be performed after the second cycle, then after every other cycle (or 8 weeks, whichever occurs first). Serial results of bone marrow aspirates, biopsies and urinary catecholamines will be reviewed for responding subjects to confirm response or lack of progression.

Clinical Response

A subject will be defined as having a clinical response if they have stable disease or better and a decrease in their tumor markers by $\geq 50\%$. Clinical response will also be defined as a subject that has a complete clearing of a previously positive bone marrow while on study.

Progression Free Survival

Time to progression, defined as the period from the first day of administration of study drug until the criteria for progression are met taking as reference the screening measurements, will be assessed.

8 Sample Size Justification

Feasibility

Since this is primarily a feasibility trial, the definition of feasibility for this study will include:

“Enrollment onto study, genomic profile, analysis and report generation completed, tumor board held with treatment decision, treatment review completed, start of treatment, and completion of 1 cycle of therapy.”

Our preliminary results for 5 subjects indicates that we have a sample collection success rate of 5/5 (100%) subjects, a genetic report profile success rate of 5/5 (100%) within the 7-10 day time window as well as a treatment agreement success rate of 5/5 (100%) within the 5 day time window. The average time (+/-SD) for completion of the genetic profile was 6.6 days (+/-1.7 days) with a median of 7 days. The average time (+/-SD) for time to Treatment was 3.2 days (+/-0.8 days) with a median of 3 days. Data preliminary to date for each of these three feasibility markers are very consistent with our anticipated performance standards.

Our initial feasibility trial continues to show that it is feasible and safe to use RNA expression analysis and a DNA mutation panel for tumor boards creating treatment decisions for patients without curative options. This study will ask the feasibility of utilizing DNA exomes and RNA sequencing in a tumor for molecular guided therapy.

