Assumptions: The feasibility outcome is a binary measure for each of the three clinical strata with a lower success null value of 50% which would require reconsideration of the full process and an upper success value of 75% for the alternative which would be deemed worthy of further consideration for an efficacy trial at the next phase. A binomial distribution was used for the testing process with a combination of Type I error levels (10%) and Power (75%). The basic design overall is a MiniMax approach which minimizes the overall sample size. **The MiniMax design with an interim look will require an overall sample size of n = 16. Each of the three clinical strata will use a two-stage decision rule.**

The Two-Stage Stopping Rule for each of the three strata is as follows:

Stage 1: Stop and accept the null hypothesis if the observed feasibility rate is less than or equal to 5/9. Otherwise, continue to stage 2.

The probability of stopping for futility is 0.746 when H_0 is true and 0.166 when H_a is true.

Stage 2: Stop and accept the null hypothesis if the observed feasibility rate is less than or equal to 10/16. Otherwise, stop and reject the null hypothesis.

As of Amendment 3.0, 100 subjects have been enrolled and all feasibility measures for all strata have been met. To gain additional feasibility with the new Drug Prediction Report and additional safety and efficacy data, additional subjects will be enrolled to meet a revised goal of 200 total evaluable subjects.

The expanded access for 100 patients will enroll following implementation of Amendment 3.0. Their tumor samples will be analyzed using an updated Drug Prediction Report (Appendix III). Overall Response Rate (ORR) and Progression Free Survival (PFS) for this group will be compared to those of the first 100 patients who received treatment based upon the original Drug Predictiton Report and Pharmacopeia Library.

9 Laboratory Evaluations

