12.3 Process and Feasibility Analysis

Each of the process measures including the total time to treatment initiation and time to completion of the first cycle of treatment will be described using standard descriptive methods such as means, medians, standard deviations, and 95% confidence intervals. The total time duration to treatment initiation and time to completion of the first cycle of treatment will also be examined using Kaplan-Meier plots since some patients who are considered process failures or who do not complete the full duration to the completion of the first cycle of treatment may contribute censored data. The formal hypothesis testing of the feasibility or success is based upon the 2-stage Mini-Max testing process outlined in Section 8: *Sample Size Justification*. Further quantification of the feasibility success rate will be based upon the percentage of the $n = 16$ patients in each strata who achieve the specified overall time frame limits. This success rate will be supplemented with an exact 95% confidence interval using a Binomial distribution model due to the small sample size involved.

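### Section 7.3 defines progression-free survival as time to progression, with no death event and no censoring rule, and its progression reference conflicts with the protocol's own PD criterion

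*Combined protocol and SAP*

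**What the plan says.** PFS is a secondary endpoint (Synopsis; Section 2.2). The only definition under its heading in Section 7.3 is "Time to progression, defined as the period from the first day of administration of study drug until the criteria for progression are met". The Synopsis gives the same interval, labelled time to progression: "period from the start of the treatment until the criteria for progression are met taking as reference the screening measurements". It then uses the term PFS without defining it.

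Section 12.4 analyses PFS by Kaplan-Meier in each stratum and explores differences from historical PFS by Cox methods when possible. It names no event and no censoring rule. The one statement on censoring, in Section 12.3, concerns time to treatment start and time to completion of cycle 1: subjects "who do not complete the full duration to the completion of the first cycle of treatment may contribute censored data".

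Two further comparisons use PFS. Section 2.2 plans "To compare PFS interval to PFS intervals of previous chemotherapy regimens since relapse for each subject". Section 8 and the Synopsis plan a cohort comparison: "Overall Response Rate (ORR) and Progression Free Survival (PFS) for this group will be compared to those of the first 100 patients".

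On the progression reference, the PFS paragraph of Section 7.3 runs "until the criteria for progression are met taking as reference the screening measurements, will be assessed". The solid-tumour PD criterion in the same section is a 20% increase with a 5 mm minimum, "taking as reference the smallest disease measurement recorded since the start of treatment (nadir", or new lesions. Duration of response also uses the nadir: "taking as reference for PD the smallest measurements recorded since the treatment started". The stable-disease definition in Section 7.3 describes the increase relative to entry.

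**The concern.** An analyst who follows Section 7.3 literally does not count a death without documented progression as an event. An analyst who follows the usual meaning of PFS counts it. Both could claim to follow the plan, and their curves would differ.

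The protocol leaves room for such deaths. The first scheduled reassessment is at the end of cycle 2 or at 8 weeks (Section 5.3.6). A final assessment is asked for only when possible (Section 7.1). Section 11.1 lists death and transfer to hospice separately from progression as reasons for stopping therapy.

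The within-subject comparison is the most exposed. A subject who lived to enrol cannot have had an earlier interval that ended in death, but the study interval can end that way. Removing those deaths from the study side tends to favour the study regimen.

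The reference conflict is a separate matter. Response and PFS could rest on different PD determinations made from the same scan.

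**Working it through.** The documents give no PFS event count, power or median, so there is no planned figure to reproduce. The figures below are illustrations under stated assumptions.

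**1. Deaths not counted: effect on the median.** Let f be the share of first events (progression or death) that are deaths without documented progression. The documents give no value, so 5% to 30% is assumed. With constant hazards, total event rate h and deaths censored at the date of death:

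- median of true PFS = ln 2 / h
- median of time to progression = ln 2 / [h(1 − f)]
- ratio = 1/(1 − f)

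| f | Median inflated by | Apparent hazard ratio against earlier regimens with the same true PFS, 1 − f |
|---|---|---|
| 5% | 1/0.95 = 1.05 | 0.95 |
| 10% | 1/0.90 = 1.11 | 0.90 |
| 20% | 1/0.80 = 1.25 | 0.80 |
| 30% | 1/0.70 = 1.43 | 0.70 |

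The last column holds because earlier intervals end only in progression and so keep the full rate h, while the study interval has rate h(1 − f).

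**2. Between cohorts.** With a true hazard ratio of 1, the apparent ratio of second to first cohort is (1 − f2)/(1 − f1). Equal shares give 1.00. Shares of 5% (first) and 10% (second) give 0.90/0.95 = 0.95. Shares of 10% and 20% give 0.80/0.90 = 0.89.

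**3. Direction without constant hazards.** If deaths are censored at the date of death, the risk sets are unchanged and there are fewer events, so the Kaplan-Meier curve is never lower. If they are censored at the last scan, subjects leave the risk set earlier and this is no longer guaranteed. Example: ten progressions at times 2, 3, ..., 11, and one death at 12 whose last scan was at 1.

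- Death as an event: 11 at risk. The curve first falls to 0.5 or below at the sixth event (5/11 = 0.45), so the median is 7.
- Death censored at 1: 10 at risk. The curve reaches 5/10 at the fifth event, so the median is 6.

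Such cases look unusual. In simulated cohorts of 100 with 8-week scans, constant hazards and f from 5% to 30% (1,000 cohorts for each f), censoring at the last scan never gave a shorter median.

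**4. Progression reference.** Apply the stated 20% and 5 mm to each reference R: threshold = max(1.2R, R + 5). Take a screening sum of 50 mm and a nadir of 35 mm.

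- Screening reference: max(60, 55) = 60 mm.
- Nadir reference: max(42, 40) = 42 mm.

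A scan at 45 mm is then PD under the criterion and for duration of response, but no event for PFS. The two references agree for a tumour that never falls below its screening size, provided the screening scan counts toward the nadir. The conflict touches only target-lesion change on CT/MRI, not new lesions, marrow or MIBG/PET.

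**The case against.** The strongest reply is that PFS is a standard term, so readers will assume that it includes death. That would carry weight if the term were undefined. Here Section 7.3 writes out a definition that ends at progression.

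A second reply is that the size is unsupported. This stands: f is an assumption, and the final assessment requested in Section 7.1 should reduce deaths without documented PD. Shrinkage large enough for a response is also likely to be a minority case. Section 1.2 cites response rates of 10% to 35% in relapsed neuroblastoma and few if any responders in relapsed CNS tumours.

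A third is weight. PFS is secondary, no PFS power or event target is stated, and the historical comparison is exploratory. This stands too, and the reference conflict alone would be a minor reconciliation point.

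Three stronger readings go too far. A reader might infer that omitting deaths can only lengthen PFS. That is assured only with censoring at the date of death, and the plan states no rule. A reader might infer that the screening reference always delays the event. It does so after shrinkage, but for a tumour that only grows it could bring the event forward if the nadir excludes the screening scan. The stable-disease wording weakens that reading without settling it. A reader might infer that the cohort comparison is biased. It is distorted only as far as the two death shares differ.

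**Conclusion.** The definition is wrong as written. What Section 7.3 calls PFS is time to progression, and no censoring rule for PFS exists. Under constant hazards and an assumed f of 5% to 30%, the median is inflated by a factor of 1.05 to 1.43, and a within-subject comparison with no true difference would show a hazard ratio of 0.95 to 0.70. The inflation is certain in direction with censoring at death, and usual but not universal with censoring at the last scan. Between cohorts it cancels when death shares are equal.

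The conflict between screening and nadir references is real, but its net size and direction cannot be estimated from the documents. A reader might take either fault as undermining the trial's main conclusion. It does not, because the two-stage feasibility test in Section 8 does not use PFS. The point should be fixed because the cohort comparison is planned and the rule ought to be settled before it is run.

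**What to change.** - **Event and censoring.** In Section 7.3, Section 12.4 and the Synopsis, define PFS as time from first study drug to the earlier of PD by the applicable Section 7.3 criteria or death from any cause, censored at the last disease assessment if neither has occurred. Also state how new therapy without PD, a regimen change after re-biopsy (Section 3.2), and death after missed scans are handled. Report time to progression, if wanted, under its own name.
- **Progression reference.** Reconcile the Synopsis entries for time to progression and duration of response with the stable-disease, PD, duration-of-response and PFS wording in Section 7.3, so that one PD determination serves all three endpoints. This point proposes no change to the clinical PD criterion, since PD ends study therapy (Section 11.1).
- **Baseline.** State which pre-treatment scan is baseline when scans are repeated after a waiting-period cycle or a gap of more than 28 days (Sections 3.6 and 5.2).
- **Within-subject comparison.** Use the death-inclusive study interval and state that earlier intervals cannot contain deaths. Report how many subjects have an earlier post-relapse interval, since some tumours are eligible at diagnosis (Section 4.1).
- **Cohorts.** Apply the same definition to both before comparing them.

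Cost: beyond the wording, a statement is needed of how long death dates are collected. The Synopsis promises survival follow-up, but the last scheduled contact is the 30-day visit (Section 5.3.7). The 100 subjects enrolled by Amendment 3.0 would need PFS re-derived and possibly death dates retrieved. Reported PFS will probably be somewhat shorter.

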9.1 Specimens to be Collected, Schedule and Amount

Required samples will be collected at the start of study. Recommended/Secondary (volunteer/optional) samples will also be collected at the start of study. Additionally, optional bone marrow samples will be collected every 6-8 weeks per Study Procedure Table.

9.2 Tumor collection and correlative biology studies.

Fresh tumor will be flash frozen and placed in kit for Ashion along with 4-6ml blood sample in an EDTA tube. Viable, fresh tumor from tumor biopsy should be placed in cell growth media using sterile technique for, cell line and xenograft generation, one vial of tumor in RNA later, and two vials of fresh frozen tumor to be shipped to the Pediatric Oncology Translational Research Laboratory for RNA analysis. Samples should be labeled with subject's study number, date of extraction and sample contents. If excess tissue is available, then snap frozen tumor tissue approximately 5mm in size should be wrapped in foil, snap frozen in liquid nitrogen and stored at -80°C. Tissue samples will be coded. Fixed tissue remaining from diagnostic evaluation may be used. Bone marrow samples will also be sent to the Pediatric Oncology Translational Research Laboratory for tumor cell isolation and culture.

At the Pediatric Oncology Translational Research Laboratory tumor cells will be grown to 70% confluence in cell growth media. Cell lines will be maintained in culture for biology studies. These will include determining the growth curves and responsiveness of cells derived from these tumors to a variety of agents identified on the report *in vitro* (both the chosen regimen as well as alternate options). Cells will be injected into the inguinal fat pad of NOD SCID mice for generation of subject xenografts. These mice will be used for correlative drug testing experiments based on predictive models. Evaluation of mechanism of action of new drug combinations will be evaluated in mice models and in cell culture through immunohistochemical staining, phosphoproteomics, PCR, and western blotting. These models will allow us the opportunity to evaluate alternate drug combinations that might have been superior to the chosen regimen.

9.3 Detailed Procedure For Sending Subject Samples:

At screening, subjects will have biopsy samples sent. The main sample for study report will be referred to as the “Primary Sample.”

The “Primary Sample” will be a current solid tumor biopsy or core bone marrow biopsy (with >50% viable tumor) along with a 4-6 mL blood sample collected in an EDTA tube.

If a solid tumor sample cannot be obtained and the subject’s bone marrow is <50% tumor then they will be ineligible for study.

In addition to the “Primary Sample”, if subjects have signed the additional consent for optional sample collection, they will also have these secondary samples sent as follows.

9.3.1 Sample Procurement and Shipping at Screening:

De-identified subject tumor samples will be sent on all subjects as following:

Label all tubes with subject’s unique identifier, date/time of sample collection, and contents (i.e. solid tumor, bone marrow, blood).

9.3.1.1 Send the following Required Primary Samples for All Tumor Types (along with appropriate form)

1. Required- Sample 1 (tumor)

Solid Tumor or Bone Marrow Core Biopsy (if solid tumor is not available)-
You will be provided a kit for tumor collection. This kit will include instructions, collection tubes and shipping instructions.

For sample 1 follow collection instructions in Appendix II (flash freeze tumor sample within 20 minutes of harvest, or sooner when possible) and ship overnight on at least 1kg of dry ice to:

*Note: Do NOT place sample in aluminum/tin foil at any time.

Ashion Analytics, LLC
[name]
[name]
[contact]
Lab [contact]
email: [contact]

For Biopsies- refer to Instructions for Core/Needle Biopsy Specimens for sample size instructions.

For Surgical resections- size of sample should be about the size of a pencil eraser. Minimum amount of tumor sample required is 50-200 mg of tissue.

2. Required- Sample 2 (blood):

Send 4-6 mL of blood in EDTA tube (ambient – prefer to have shipped on frozen gel pack in summer months May to October) to:

Ashion Analytics, LLC
[name]
[name]
[contact]
Lab [contact]
email: [contact]

9.3.1.2 Send the following Recommended secondary tumor samples along with appropriate forms listed in order of priority (please work your way down the list of tumor samples until you either run out of available sample or have completed all samples. Once this occurs move on to Bone Marrow samples):

You will be provided a kit for tumor collection (fresh snap frozen and in culture media). Follow collection instructions and ship as directed overnight.

3. Sample 3:

With sterile technique and within 20 minutes add tumor sample or needle core biopsy to T25 flask containing cell growth media (provided), seal with parafilm, and overnight at ambient temperature to:

[name]
Pediatric Oncology Translational Research Laboratory
[name]
[name]
[name]
Ph: [contact]
[contact]

4. Sample 4:

Add tumor or needle core biopsy to cryo-vial, snap freeze and ship on at least 1kg of dry ice to:

[name]
Pediatric Oncology Translational Research Laboratory
[name]
[name]
[name]
Ph: [contact]
[contact]

5. Sample 5:

Add tumor or needle core biopsy to cryo-vial, snap freeze and ship on at least 1kg of dry ice to:

[name]

Pediatric Oncology Translational Research Laboratory
[name]
[name]
[name]
Ph: [contact]
[contact]

6. Sample 6:

Add tumor or needle core biopsy to RNA Later and ship overnight at ambient temperature to:

[name]

Pediatric Oncology Translational Research Laboratory
[name]
[name]
[name]
Ph: [contact]
[contact]

9.3.1.3 For all Tumor Types: Send the following Recommended secondary blood sample (along with appropriate forms):

Blood- Send 4-6 mL of blood in tubes (tubes and instructions will be provided).

1. Sample 7:

Send PAX DNA Gene tubes (ambient) to:

[name]

Pediatric Oncology Translational Research Laboratory
[name]
[name]
[name]
Ph: [contact]
[contact]

**9.3.1.4 For Neuroblastoma Subjects or Any subject with suspected bone marrow disease
Only- Send the following Recommended secondary bone marrow samples listed in
order of priority (along with appropriate forms):**

1. Sample 8:

Bone Marrow Aspirate- Send 4 mL of bone marrow aspirate (preferably bilateral) in green top (sodium heparin) tube(s) priority overnight at room temperature to:
(Please alert site 2-3 days prior to procedure. Contact site to confirm shipment as well.)

[name]
Pediatric Oncology Translational Research Laboratory
[name]
[name]
[name]
Ph: [contact]
[contact]

Notes: If all samples are collected, you will be collecting 8 samples and mailing **4** packages. The samples above are listed in decreasing priority.

* Sample 1 to Ashion (frozen on dry ice)
** Sample 2 to Ashion (ambient with frozen gel pack)
***Sample 3, 6, 7, & 8 to Pediatric Oncology Translational Research Laboratory (ambient).
****Samples 4 & 5 to Pediatric Oncology Translational Research Laboratory (frozen).

***** Keep collection flask (sample 3) at 4° C. until ready to use.

Please contact [name] if you have any trouble with the preparation or packaging of the samples. [contact]

**9.3.2 For Neuroblastoma Subjects or Any subject with suspected bone marrow disease
Only- Sample Procurement and Shipping at the end of Cycle 2 and every two cycles
after that:**

Send the following Recommended samples (along with appropriate forms) to the
Pediatric Oncology Translational Research Laboratory

1. **Bone Marrow Aspirate-** Send 4 mL of bone marrow aspirate (preferably bilateral) in green top (sodium heparin) tube(s) priority overnight at room temperature to:

[figure not shown]
[name]

Pediatric Oncology Translational Research Laboratory
[name]
[name]
[name]
Ph: [contact]
[contact]

